3.4.2 Surgical Variables

The following variables will be recorded preoperatively, intraoperatively, or postoperatively:

- Date/time of hospital admission;
- Body weight (kg or lbs; no shoes);
- Body height (cm or in; no shoes);
- Procedure duration, defined as first skin incision to final skin closure;
- Did vessel skeletonization occur (Yes/No; if Yes, describe vessel skeletonized and device used);
- Was there presence of inflamed tissue, calcified tissues/vessels, atherosclerotic tissue, fibrotic tissue, or presence of adhesions, if applicable (Yes/No; if Yes, describe the tissue along with location);
- Were adhesions removed or divided by ENSEAL X1 (Yes/No; if Yes, describe adhesions along with location and complete 5-point scale);
- Were lymphatics and tissue bundles divided by ENSEAL X1 (Yes/No; if Yes, describe lymphatics and tissue bundles along with location and complete 5-point scale);
- Was ENSEAL X1 used for grasping tissue, tissue cutting, or tissue dissection (Yes/No; if Yes, describe activity along with location and complete 5-point scale);
- Conversion to open with reason, if applicable;
- Volume of estimated intra-operative blood loss;
- Use of any other energy device (monopolar, traditional bipolar, advanced bipolar, ultrasonic) in primary procedure (type, name, and number of device and reason for use), if applicable;
- Name, product code, and number of Ethicon trocars used with ENSEAL X1, if applicable;
- Was there prophylactic use of clips as standard of surgical care before vessel transection (Yes/No; if Yes, name vessel transected, and number of clips prophylactically applied);
- For each vessel transected with ENSEAL X1:
 - Name of each vessel;
 - Hemostasis grading scale assessment;
 - Surgeon determination of diameter size range (< 3 mm, 3 to 5 mm, and > 5 to 7 mm);
 - Image captured where the vessel is perpendicular and below the open jaw of the ENSEAL X1 device;
 - For every Grade 3 vessel transection:
 - Compression used as a mild intervention, if applicable (Yes/No);
 - Touch-ups with a monopolar device, if applicable (Yes/No; if Yes, record number of touch-ups);

- Touch-ups with a bipolar device, if applicable (Yes/No; if Yes, record number of touch-ups);
- Touch-ups with ENSEAL X1 (Yes/No; if Yes, record number of touch-ups);
- For every Grade 4 vessel transection intervention:
 - Type, name, and number of times used for each additional hemostatic measure used along with a description of why it was considered Grade 4;

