5.6 ANALYSIS SETS

The summary of all performance and safety endpoints will be performed on the set of subjects in whom the ENSEAL X1 device is utilized during the surgical procedure. The summary of all performance and safety endpoints will be performed by procedure group and procedure subgroup on the entire pooled set of subjects. The hypotheses described in Section 5.4 will be evaluated on the pooled set of subjects as data on the ENSEAL X1 Large Jaw device demonstrated consistent performance across procedure groups in a similar study (>94% Grade 3 or lower hemostasis achieved for each procedure group).

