1.2 Study Design

This prospective, single-arm, multi-center study will collect clinical data in a post-market setting by procedure group (upper gastrointestinal (GI), lower GI, and gynecological). Investigators will perform each procedure using the device in compliance with their standard surgical approach and the ENSEAL X1 and GEN11 IFUs.

Subjects will be consented and screened anytime during a period of 8 weeks prior to the date of surgery. Subjects will be considered enrolled when the ENSEAL X1 device has been attempted to be used for a vessel transection during upper GI, lower GI, or gynecological procedures. All enrolled subjects will be followed post-operatively through discharge and again at 28 days (\pm 14 days) post-surgery; therefore, from the surgery date to study exit, the duration will be approximately 6 weeks.

A minimum of 133 subjects (maximum of 149 subjects) will be included in the study from up to 16 surgery centers in the United States and/or European Union and/or United Kingdom. The enrollment is planned with the following procedure targets:

- A minimum of 77 subjects enrolled to a maximum of 89 subjects enrolled for upper GI procedures to achieve 27 vessel transections in each of the four procedure subgroups.
 Subjects will be enrolled to the following procedure subgroups with corresponding enrollment restrictions:
 - A minimum of 14 subjects enrolled to a maximum of 17 subjects enrolled for fundoplication (Nissen, anterior or posterior [Toupet]) or hiatal hernia procedures);
 - A minimum of 27 subjects enrolled to a maximum of 30 subjects enrolled for gall bladder procedures;
 - A minimum of 10 subjects enrolled to a maximum of 13 subjects enrolled for sleeve gastrectomy procedures;
 - A minimum of 26 subjects enrolled to a maximum of 29 subjects enrolled for small intestine resection procedures (also includes Roux-en-Y gastric bypass [RYGB] and biliopancreatic diversion with duodenal switch [BPD/DS]);
- A minimum of 28 subjects enrolled to a maximum of 30 subjects enrolled for lower GI procedures (e.g., large intestine resections); and
- A minimum of 28 subjects enrolled to a maximum of 30 subjects enrolled for gynecological procedures (hysterectomies associated with oophorectomies).

2 Treatment Assignment

This is a single-arm study where all enrolled subjects will have the ENSEAL X1 device utilized for transection of at least one vessel.

3 Randomization and Blinding Procedures

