As this is a single-arm study, no randomization will occur, and no blinding procedures are required.

4 Interval Windows

Interval windows for the purpose of analysis in this study will not be defined outside of those already specified in the protocol for visit scheduling as the collection of data for the primary and secondary performance endpoints occurs intra-operatively. The final visit occurs approximately 4 weeks after surgery, thus no interval windows need to be defined given the absence of long-term follow-up in this study. The Schedule of Events specifies a window of 14 days around the scheduling of the 4-week follow-up visit, and any information entered in the eCRFs at this visit will correspond to the 4-week visit. There will be no assigning of observations to time points outside of the visit to which they are recorded in the eCRFs.

5 Levels of Significance

The statistical hypothesis for the primary endpoint will be evaluated using a one-sided significance level of 0.025. A 95% confidence interval will be provided for the primary endpoint. Estimation of primary endpoint by procedure group and procedure subgroup will provide 95% confidence interval. Estimation of secondary and safety endpoints will be summarized by number and percentages only.

6 Analysis Sets

Full Analysis Set: Full Analysis Set (FAS) will include subjects for whom the ENSEAL X1 device is utilized during the surgical procedure and have assessment for the primary endpoint. The FAS includes subjects for whom the answer is "Yes" to at least one of the following questions from the "ENSEAL X1 Usage" form on eCRF: "Were adhesions removed or divided by ENSEAL X1", "Were lymphatics bundles divided by ENSEAL X1", "Were tissue bundles divided by ENSEAL X1", "Was the ENSEAL X1 used for tissue grasping", "Was the ENSEAL X1 used for tissue dissection." The summary of all primary and secondary performance endpoints will be performed using FAS by procedure group (upper GI, lower GI, and gynecological), procedure subgroup (fundoplication, gall bladder, sleeve gastrectomy, and small intestine resection) and on the entire pooled set of subjects.

Safety Analysis Set: The Safety Analysis Set (SAS) will include all subjects who signed informed consent and for whom the ENSEAL X1 device is utilized during the surgical procedure. The safety endpoints will be summarized using SAS by procedure group, procedure subgroup and in total.

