8.4 Primary and Secondary Endpoints and Associated Hypotheses

8.4.1 Primary Endpoint and Associated Hypotheses

The primary performance endpoint in this study is the number and percentage of vessels where hemostasis (\leq Grade 3) is achieved using the ENSEAL X1 device. The hemostasis grading scale is defined as:

- Grade 1: no bleeding at transection site;
- Grade 2: minor bleeding at transection site, no intervention needed;
- Grade 3: minor bleeding at transection site, mild intervention needed, use of compression, basic energy devices (monopolar and/or bipolar device), and/or touchups with ENSEAL X1.
- Grade 4: significant bleeding (e.g., pulsatile blood flow, venous pooling) requiring intervention such as extensive coagulation or ligation with use of additional hemostatic measures (e.g., hemoclips, staples, sutures, fibrin sealants, other advanced energy products).

The primary performance endpoint will be summarized at the vessel transection level as multiple vessel transections per subject is expected; that is, the denominator for the primary endpoint will be the total number of vessel transections and the numerator will be the number of vessel transections where hemostasis (\leq Grade 3) is achieved.

The following hypothesis will be evaluated for the primary endpoint:

H₀:
$$p \le 87.5\%$$

H₁: $p > 87.5\%$

Where *p* is the percentage of transections achieving a Grade 3 or lower hemostasis rating and 87.5% is set as a performance goal for the lower bound of acceptable hemostasis. A 95% confidence interval will be calculated for *p* based on the proportion of vessel transections where Grade 3 or lower hemostasis is achieved using Clopper-Pearson's method and the lower limit of this confidence interval will be compared to 87.5% to evaluate the above hypotheses. A p-value will be determined based on an exact binomial test. Primary endpoint will be evaluated for the total sample. For procedure group and procedure subgroup 95% CI will be provided using Clopper-Pearson's method for proportion of vessel transections where Grade 3 or lower hemostasis is achieved.

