8.4.2 Secondary Endpoints and Associated Hypotheses

No formal hypotheses are specified for the secondary endpoints of this study.

Counts and percentages will be provided for the following secondary endpoints:

• Categories of 5-point scale scores for various tasks completed by the ENSEAL X1 device (adhesion removal or division, lymphatics or tissue bundles divided, tissue grasping, tissue cutting, or tissue dissection). The scale will be a 5-point scale (very dissatisfied, dissatisfied, neither satisfied or dissatisfied, satisfied, or very satisfied) asking how

- satisfied the surgeon was with the use of the device for each of the tasks as collected on the "ENSEAL X1 Usage form in eCRF;
- Categories of hemostasis grading scale for each vessel transected; and
- Type, name, and number of additional hemostasis products required to achieved hemostasis for Grade 4 vessel transections.

Counts and percentages will also be provided for type, size, and number of vessels transected. Listing will be provided for ENSEAL X1 usage and vessel transected forms.

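### SAP section 6 gives two conflicting rules for the Full Analysis Set; the second, used as a filter, would drop graded vessels from the primary test

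*SAP*

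**What the plan says.** SAP section 6 (Analysis Sets) describes the FAS in two consecutive sentences.

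- **Sentence 1:** the FAS "will include subjects for whom the ENSEAL X1 device is utilized during the surgical procedure and have assessment for the primary endpoint".
- **Sentence 2:** "The FAS includes subjects for whom the answer is 'Yes' to at least one of the following questions". The questions come from the ENSEAL X1 Usage form and cover adhesions, lymphatic bundles, tissue bundles, tissue grasping and tissue dissection.

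The same section assigns all primary and secondary performance endpoints to the FAS. It does not say how the two sentences combine.

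Other parts of the plan rest on vessel transection:

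- SAP 1.2: "Subjects will be considered enrolled when the ENSEAL X1 device has been attempted to be used for a vessel transection".
- SAP section 2 expects every enrolled subject to have at least one vessel transected with the device.
- SAP 8.4.1: "the denominator for the primary endpoint will be the total number of vessel transections".
- Protocol 5.6 applies no task filter: "The summary of all performance and safety endpoints will be performed on the set of subjects in whom the ENSEAL X1 device is utilized".

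On the forms, SAP 8.4.2 separates task use from vessel data: "Listing will be provided for ENSEAL X1 usage and vessel transected forms". The tasks it scores from the Usage form include "lymphatics or tissue bundles divided, tissue grasping, tissue cutting, or tissue dissection". Protocol 3.4.2 likewise collects cutting as a yes/no item: "Was ENSEAL X1 used for grasping tissue, tissue cutting, or tissue dissection".

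**The concern.** The two sentences select different subjects. Someone with graded vessels who has No for all five tasks meets sentence 1 and fails sentence 2. So does someone in whom the device, beyond transecting vessels, was used only to cut tissue. Sentence 2 is the one that names eCRF fields, which makes it a natural candidate for the programmed filter.

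The FAS carries the study's only formal hypothesis test. Under the filter, the primary denominator would depend on answers to questions unrelated to hemostasis at the transection site, and a borderline result could move either way. If the wording stays open, the choice falls to the programming stage. In an open-label, single-arm study the hemostasis grades may already be visible by then.

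**Working it through.** **Step 1. Compare the rules.**

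| Subject | Sentence 1 | Sentence 2 |
|---|---|---|
| Graded vessel, Yes to at least one listed task | in | in |
| Graded vessel, No to all five | in | out |
| Graded vessel, tissue cutting the only other use | in | out |
| No graded vessel, Yes to grasping | out | in |

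The last row adds nothing to the vessel numerator or denominator. The second and third rows remove vessels from the primary test. The removal occurs whether sentence 2 is read as the definition, as an added condition, or as the meaning of device use. It is avoided only if the word includes is illustrative, which the SAP does not state.

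**Step 2. Inputs.** Goal p0 = 0.875 (SAP 8.4.1). Expected rate 0.94, one-sided alpha 0.025, 230 vessels and 1.9 vessels per subject (SAP 7). Minimum 133 subjects (SAP 1.2), so 133 × 1.9 = 252.7, about 253 vessels. The share of vessels dropped is not in the documents and is assumed below.

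**Step 3. Reproduce the stated power.** The pass line is the smallest r with P(X ≥ r | n, 0.875) ≤ 0.025; power is P(X ≥ r | n, 0.94). For n = 230, r = 212, the attained level is 0.0161 and power is 0.9002. The stated minimum of 90% reproduces.

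**Step 4. Borderline results.** Clopper-Pearson 95% lower bound and exact one-sided p:

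| Result | Lower bound | p | Verdict |
|---|---|---|---|
| 211/230 | 87.40% | 0.0277 | fail |
| 211/229 (one Grade 4 vessel dropped) | 87.86% | 0.0171 | pass |
| 212/230 | 87.91% | 0.0161 | pass |
| 204/222 (eight Grade 3-or-lower vessels dropped) | 87.49% | 0.0253 | fail |
| 232/253 | 87.59% | 0.0226 | pass |
| 230/251 (two Grade 3-or-lower vessels dropped) | 87.495% | 0.0251 | fail |

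Eight vessels are about four subjects (8 / 1.9 = 4.2).

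**Step 5. How often the verdicts differ.** Let K be successes among kept vessels and D successes among dropped vessels, independent binomials with the same rate. The verdicts differ when exactly one of these holds: K + D reaches the full-set pass line, or K reaches the filtered-set pass line.

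| Vessels | Dropped (assumed) | True rate 94% | True rate 92% (assumed) |
|---|---|---|---|
| 230 | 5 (2%) | 1.5% | 3.9% |
| 230 | 12 (5%) | 3.1% | 6.8% |
| 230 | 23 (10%) | 4.9% | 10.0% |
| 253 | 5 (2%) | 2.2% | 6.3% |
| 253 | 13 (5%) | 3.9% | 10.3% |
| 253 | 25 (10%) | 4.9% | 12.5% |

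**Step 6. Power at 94%.**

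| Vessels analyzed | Power |
|---|---|
| 253 | 94.7% |
| 230 | 90.0% |
| 223 to 229 | 90.3% to 92.0% |
| 222 | 87.9% |
| 218 | 89.3% |
| 207 | 88.1% |

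Exact power moves in a saw-tooth, so falling below 230 does not by itself lose 90% power.

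**The case against.** Most of the plan points to the benign reading. Sentence 1 can itself be programmed, because the endpoint assessment is the grade recorded for each vessel. The denominator in SAP 8.4.1, the enrollment rule and Protocol 5.6 all agree with it, and sentence 2 does not say only. **This stands in part:** it shows what was probably intended, but it also shows that the list, applied as written, contradicts the rest of the plan.

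The number affected may be zero, since grasping and tissue bundles are on the list and the jaws are designed to grasp. **This stands.** Every frequency above rests on an assumed share.

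The flip examples sit at the pass line. At a true 94%, exactly 211/230 has probability 3.7% and exactly 212/230 has 5.2%. From 212/230, dropping up to seven successes still passes. If the loss is unrelated to grade, the test keeps its 0.025 level under either set, so a differing verdict is not a false-positive rate. Some differences favor passing: 1.2 of the 3.1 points at 230 vessels with 5% dropped. A 10% loss from 253 leaves 228 vessels with 90.6% power. **All of this stands** and limits the size of the point.

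Safeguards exist: the protocol requires SAP approval before database lock, all eCRF data are listed, and departures from the SAP are to be documented. They would make an exclusion visible, but they do not settle which rule applies.

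**Conclusion.** The concern holds. The five-task list is a wrong membership rule as written, because it omits the act that generates the primary endpoint; it also omits tissue cutting, which the same form scores. Used as the filter, it removes graded vessels from the only formal test.

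The size is uncertain and probably limited. For assumed losses of 2% to 10% of vessels unrelated to grade, the two rules disagree in 1.5% to 4.9% of trials at a true rate of 94%, and in 3.9% to 12.5% at an assumed 92%. From 230 vessels, power goes from 90.0% to 89.3% at a 5% loss and 88.1% at 10%. These figures assume independent vessels and equal rates in kept and dropped vessels. The documents give no basis for the direction of any bias. The point should be fixed before lock, mainly so that membership of the primary set is settled without reference to the grades.

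**What to change.** In SAP section 6:

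1. Define the FAS as all subjects with at least one primary-procedure vessel transection attempted with ENSEAL X1 that has a hemostasis grade on the vessel-transected form. Limiting it to the primary procedure matches Protocol 3.4.2, which keeps concomitant-procedure vessels out of the primary endpoint.
2. Delete the five-question rule from FAS membership.
3. Use the Usage-form questions, with tissue cutting added, only as denominators for the matching 5-point task scores.
4. List any attempted transection that has no grade, with the reason.

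The cost is one SAP edit and one programming filter before database lock. No new data are needed, and if no subject is affected the results do not change.

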 11 NOV 2022

utilizing consecutive screening and enrollment in an effort to generate a random and representative patient population sample. All eligible subjects (Sections 3.2.3 and 3.2.4) will be considered enrolled at the time when the ENSEAL X1 device has been attempted to be used for a vessel transection during one of the proposed procedure groups. Up to 16 surgery centers (United States and/or European Union and/or United Kingdom) will be selected as study sites. Each participating investigator is expected to perform a minimum of two procedures using the ENSEAL X1 device. A minimum of 133 subjects (maximum of 149 subjects) will be included in the study to achieve a total of 230 vessel transections. The enrollment is planned with the following procedure targets:

- A minimum of 77 subjects enrolled to a maximum of 89 subjects enrolled for upper GI procedures which will contain the following subgroups with corresponding enrollment restrictions:
 - A minimum of 14 subjects enrolled to a maximum of 17 subjects enrolled for fundoplication (Nissen, anterior or posterior [Toupet]) or hiatal hernia procedures);
 - A minimum of 27 subjects enrolled to a maximum of 30 subjects enrolled for gall bladder procedures;
 - A minimum of 10 subjects enrolled to a maximum of 13 subjects enrolled for sleeve gastrectomy procedures;
 - A minimum of 26 subjects enrolled to a maximum of 29 subjects enrolled for small intestine resection procedures (also includes RYGB and BPD/DS),
- A minimum of 28 subjects enrolled to a maximum of 30 subjects enrolled for lower
 GI procedures (e.g., large intestine resections); and
- A minimum of 28 subjects enrolled to a maximum of 30 subjects enrolled for gynecological procedures (hysterectomies associated with oophorectomies). The planned use of the ENSEAL X1 device should be for both the hysterectomy and oophorectomy steps of the procedures.

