5.7 SAMPLE SIZE JUSTIFICATION

A sample size of at least 230 vessel transections is required to have a minimum of 90% power for rejecting the null hypothesis when the expected rate of Grade 3 hemostatic transections is at least 94.0% based on exact binomial test and a one-sided significance level of 0.025. The hemostatic transection grades for vessels are assumed to be independent within a subject and procedure.

In order to achieve a total of 230 vessel transections for analysis with a minimum of 27 vessel transections in each group (including 4 subgroups in upper GI procedure), a minimum of 133 subjects (a maximum of 149 subjects) will be enrolled in the study.

The original sample size of the study was based on the assumption of one vessel transection per subject. At the time of amendment 5 the number of transections per subject was estimated to be 1.9 on average. The primary endpoint and the study hypothesis are based on hemostasis of vessel transection; therefore, the number of subject to be enrolled was updated to ensure 230 vessel transections.

Given that the primary endpoint is being evaluated intra-operatively, it is not anticipated that there will be subject dropout prior to evaluating this endpoint, thus no adjustment or increase in subject enrollment is planned to account for dropout. A minimum of 27 vessel transections in each group (including 4 subgroups in upper GI procedure) is planned to attain optimum representation of each of the procedure groups to the whole study sample.

From a safety perspective on the pooled analysis of 133 subjects and in consideration of rare AEs that may occur (e.g., bleeding requiring blood product transfusion), for an event that has an incidence rate of, for example, 1%, then in a sample of 133 subjects, the probability of observing at least 1 event is 73.7% under a binomial probability model. Thus, this sample size provides a high probability of observing rare events if they do occur, and provides reasonable assurance to conclude that the likelihood of such AEs is less than 2.8% if they do

not occur based on the upper limit of an exact 95% confidence interval when 0 events out of 133 subjects are observed.

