All Enrolled Set: The All Enrolled Set (AES) contains all subjects who provide informed consent for this study. The AES will be used for disposition of study subjects and for all listings.

7 Sample Size Justification

A sample size of at least 230 vessel transections is required to have a minimum of 90% power for rejecting the null hypothesis when the expected rate of Grade 3 hemostatic transections is at least 94.0% based on exact binomial test and a one-sided significance level of 0.025. The hemostatic transection grades for vessels are assumed to be independent within a subject and within a procedure.

In order to achieve a total of 230 vessel transections for analysis with a minimum of 27 vessel transections in each group (including 4 procedure subgroups in upper GI procedure), a minimum of 122 subjects (a maximum of 149 subjects) will be enrolled in the study.

The original sample size of the study was based on the assumption of one vessel transection per subject. At the time of amendment 5 the number of transections per subject was estimated to be 1.9 on average. The primary endpoint and the study hypothesis are based on hemostasis of vessel transection; therefore, the number of subject to be enrolled was updated to ensure 230 vessel transections.

Given that the primary endpoint is being evaluated intra-operatively, it is not anticipated that there will be subject dropout prior to evaluating this endpoint, thus no adjustment or increase in subject enrollment is planned to account for dropout. A minimum of 27 vessel transections in each group (including 4 procedure subgroups in upper GI procedure) is planned to attain optimum representation of each of the procedure groups to the whole study sample.

From a safety perspective on the pooled analysis of 133 subjects and in consideration of rare AEs that may occur (e.g., bleeding requiring blood product transfusion), for an event that has an incidence rate of, for example, 1%, then in a sample of 133 subjects, the probability of observing at least 1 event is 73.7% under a binomial probability model. Thus, this sample size provides a high probability of observing rare events if they do occur, and provides reasonable assurance to conclude that the likelihood of such AEs is less than 2.8% if they do not occur based on the upper limit of an exact 95% confidence interval when 0 events out of 133 subjects are observed.

8 Analyses to be Conducted

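### SAP Section 7 gives a minimum of 122 subjects; the protocol, SAP 1.2 and the plan's own group minimums all give 133

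*SAP*

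**What the plan says.** SAP Section 7 asks for 230 vessel transections overall and at least 27 in each procedure group, counting the four upper GI subgroups separately. To meet both aims it states that "a minimum of 122 subjects (a maximum of 149 subjects) will be enrolled in the study".

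The other statements of the minimum differ:

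- SAP 1.2: "A minimum of 133 subjects (maximum of 149 subjects) will be included in the study from up to 16 surgery centers".
- Protocol 5.7, in a sentence that otherwise matches the one in SAP Section 7: "a minimum of 133 subjects (a maximum of 149 subjects) will be enrolled in the study".
- Protocol 3.2.1: "A minimum of 133 subjects (maximum of 149 subjects) will be included in the study to achieve a total of 230 vessel transections". The protocol synopsis also gives 133.

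The safety paragraph of SAP Section 7 itself uses 133. It opens "From a safety perspective on the pooled analysis of 133 subjects" and derives its 73.7% and 2.8% figures from that number.

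SAP 1.2 and Protocol 3.2.1 list minimum and maximum enrolment by procedure. Upper GI is 77 to 89, made up of fundoplication or hiatal hernia 14 to 17, gall bladder 27 to 30, sleeve gastrectomy 10 to 13 and small intestine resection 26 to 29. Lower GI and gynecological procedures are each 28 to 30.

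**The concern.** The SAP holds two different minimum sample sizes, and the lower one stands in the section that is meant to justify the number. It does not follow from the purpose given in its own sentence, and it disagrees with the figure used for safety precision later in that section. A reader who takes SAP Section 7 at face value would accept a study of 122 subjects as complete. At least one procedure would then be below its enrolment minimum, and the printed safety probability and upper bound would not apply.

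**Working it through.** **Inputs.** Enrolment ranges by procedure: SAP 1.2 and Protocol 3.2.1. Required vessels 230 and average of 1.9 transections per subject: SAP Section 7 and Protocol 5.7. Performance goal 87.5%: SAP 8.4.1. Expected rate 94.0% and one-sided significance level 0.025: SAP Section 7. No allowance for dropout is planned.

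**1. Sum of the enrolment limits.**

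- Upper GI minimum: 14 + 27 + 10 + 26 = 77, as stated.
- Overall minimum: 77 + 28 + 28 = 133.
- Overall maximum: 17 + 30 + 13 + 29 = 89, and 89 + 30 + 30 = 149, as stated everywhere.

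The maximum of 149 in the SAP Section 7 sentence follows from this list. The minimum of 122 does not: 133 − 122 = 11 subjects short, or 11/133 = 8.3%.

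**2. Where 122 may come from.** 230/1.9 = 121.05, which rounds up to 122. The documents do not say this, so it is an inference. It would make 122 the number of subjects for the total vessel count only.

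**3. Safety figures.** The chance of at least one event at 1% incidence is 1 − 0.99^n. The upper limit of the exact two-sided 95% interval with no events is 1 − 0.025^(1/n).

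| n | P(at least one event) | Upper limit, 0 events |
|---|---|---|
| Printed | 73.7% | less than 2.8% |
| 133 | 73.7% | 2.74% |
| 122 | 70.7% | 2.98% |

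Both printed figures reproduce at 133. Neither holds at 122.

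**4. Expected vessels at 1.9 per subject.**

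- 133 × 1.9 = 252.7, which is 22.7 above 230.
- 122 × 1.9 = 231.8, which is 1.8 above 230.

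The documents give no standard deviation for vessels per subject. If it is assumed to lie between 0.5 and 1.5 (normal approximation with continuity correction), the chance of ending below 230 vessels is about 34% to 44% with 122 subjects. With 133 it is from below 0.01% to about 9%.

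**5. Primary power.** With 230 vessels the exact test needs at least 212 successes. Its exact one-sided level is 0.0161 and its power at 94.0% is 90.02%, as the plan states. This does not depend on the number of subjects.

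**The case against.** The inconsistency itself is not in doubt; the case against is that it matters little.

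- **The protocol governs enrolment.** It gives 133 and every group minimum, and SAP 1.2 repeats them. Nothing makes SAP Section 7 a stopping rule. This stands, and it makes an actual stop at 122 unlikely. It does not remove the contradiction within the SAP.
- **The SAP Section 7 sentence promises 27 vessels per group, not a number of subjects.** Six groups of 27 need 162 vessels, and 122 subjects are expected to yield 231.8. If all 11 missing subjects came from lower GI and gynecological procedures, leaving 22 and 23, about 1.2 vessels per subject would still give 27 in each. The documents give no vessel average by group, so a vessel shortfall cannot be shown. This also stands. What 122 certainly misses is a subject minimum.
- **The safety figures are correct as printed,** because their paragraph names 133. They are also illustrative, with no safety hypothesis attached. That is true, but it confirms that 133 is the number the section relies on.
- **The primary hypothesis, test and power are untouched.** This stands in full.

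**Conclusion.** The concern holds. The 122 in SAP Section 7 is wrong as written. It conflicts with SAP 1.2, with the protocol and with the safety paragraph of its own section, and it is 11 subjects below the sum of the plan's enrolment minimums. At 122 the safety probability would be about 3 percentage points lower than printed, and the upper limit would be 2.98%, above the stated 2.8%. The expected margin over 230 vessels would fall from about 23 to about 2, if the pooled average of 1.9 holds for the final case mix.

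The effect is limited to the stated sample size, the group minimums and the safety precision. No loss of power at 230 vessels and no change in type I error follow. The contradiction and the sums rest on the documents alone; only the origin of 122 is inferred.

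**What to change.** In SAP Section 7, replace 122 with 133. Add a clause saying that 133 is the sum of the group enrolment minimums (77 + 28 + 28), which the protocol synopsis bases on enrolment at amendment 5 and the projected need for 27 vessels per group. If the sponsor confirms the origin of 122, the text can add that 230/1.9 = 121.05, rounded up to 122, is the requirement for total vessels alone and does not set the minimum.

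The cost is one number and one clause in the SAP, to be made before database lock. The protocol, the safety figures and the power statement need no change on this account.
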